Expeditious, safe extubation is vitally important in the care of Intensive Care Unit (ICU) patients, as prolonged mechanical ventilation harms patients and failed extubation (i.e. re-intubation within 48 hrs) is associated with increased morbidity, mortality and costs. The urgent need to improve extubation failure is further highlighted by current observations suggesting that COVID-19 patients are at increased risk of both early and late extubation failure. We previously found that decreased respiratory rate variability (indicative of reduced adaptability and/or increased stress) during Spontaneous Breathing Trials (SBTs) predicted extubation failure and outperformed the best available predictive indices. Combining this predictive analytic with standardized extubation readiness checklists and risk mitigation strategies, we created the **Extubation Advisor™** (EA). We recently completed a single-center phase I mixed methods observational study (n=117) wherein we demonstrated technical feasibility (i.e. ability to generate 92% of EA reports) and clinician acceptance of the EA tool. In the current open-label, multi-center interventional phase I study, we will assess the feasibility and initial perceptions of EA implementation in the intensive care unit by (1) evaluating the feasibility of patient enrolment, data collection, and EA report generation, and (2) performing a mixed-methods analysis of critical care physician and respiratory therapist perceptions of EA. Findings from this study will inform a future randomized controlled trial assessing EA outcomes compared to standard of care, with the intent of aiding bedside decision-making, enhancing care delivery, and improving outcomes in critically ill patients with and without COVID-19.

Table of Contents

Site Investigator Signature Page	2
1. Brief Summary	3
2. Background	6
2.1. Background and rationale for clinical implementation of Extubation Advisor	6
2.2. Background and rational for mixed-methods analysis	8
3. Conflict of Interest	8
4. Research Question	9
5. Objectives	9
6. Study Outcomes	9
7. Design	9
8. Centers	10
9. Sample Size and Timeline	10
9.1. Sample size for clinical implementation of Extubation Advisor	10
9.2. Sample size for mixed-methods analysis	10
10. Eligibility	10
10.1. Inclusion and Exclusion Criteria for Patient Participants	10
10.2. Inclusion and Exclusion Criteria for Extubation Advisor Users	11
10.3. Co-enrolment	11
11. Study Procedure	12

2.1. Background and rationale for clinical implementation of Extubation Advisor

Expeditious and safe extubation (endotracheal tube removal) in critically ill patients is a vitally important transition from life support to spontaneous breathing. Prolonged invasive ventilation and failed extubation (i.e. re-intubation <48 hrs; 15% incidence) are associated with increased morbidity, mortality, cost, and increased risk to health care personnel due to aerosolization¹⁻⁶.

Intensive Care Units (ICUs) globally now face the additional challenge of treating COVID-19 patients, with record numbers of patients requiring ventilator support. Current data support that 60-75% of COVID-19 patients admitted to the ICU present with acute respiratory distress syndrome (ARDS) and respiratory failure requiring intubation and invasive ventilation⁷. Although no published data have characterized the epidemiology (incidence, causes, consequences) of extubation failure, ICU clinicians worldwide have identified on various social media platforms that critically ill patients afflicted with COVID-19 have an increased incidence of extubation failure.

For critically ill patients, a spontaneous breathing trial (SBT) is the current standard of care to assess 'extubation readiness'. SBTs are focused assessments of a patient's ability to tolerate minimal ventilatory support over 30-120 minutes and are performed by respiratory therapists (RTs) working collaboratively with ICU physicians to oversee ventilator management in the ICU. A rapid shallow breathing pattern during an SBT is worrisome and portends failure. Nevertheless, even the most widely used measurement, the respiratory frequency to tidal volume ratio also known as the rapid shallow breathing index (RSBI), has limited value in predicting whether patients will be successfully extubated⁸⁻¹⁰.

Recognizing the implications of a failed attempt at extubation to patients and healthcare systems, significant interest has emerged in identifying strategies that aid bedside clinicians to better predict extubation success and failure¹¹⁻¹⁶. ICU clinicians typically monitor critically ill patients using waveforms (e.g. electrocardiography, capnography, oxygen saturation, etc.). Although waveform data is sampled hundreds of times per second, vital signs are commonly charted per hour, thus ignoring valuable information regarding the complexity or variability of the heart or breathing rate. Decreased heart rate variability (HRV) and respiratory rate variability (RRV) are associated with illness, age, and stress, indicating reduced adaptability and physiologic reserve. Variability analysis documents degree and character of fluctuations of these physiologic parameters over intervals-in-time. Several small studies have demonstrated that reduced HRV or RRV during SBTs is associated with extubation failure¹⁷⁻²³.

In 2014, we completed and published the large, prospective, observational, multicenter Weaning and Variability Evaluation (WAVE) study (n=721) addressing the ability of HRV and RRV to predict extubation outcomes in a heterogeneous cohort of invasively ventilated critically ill patients²⁴. We found that both reduced HRV and RRV during SBTs were associated with extubation failure ($p<0.007$) and derived a predictive model, known as the WAVE score, based on an average ensemble of logistic regression models including 5 measures of RRV. More importantly, the WAVE score demonstrated high and complementary predictive accuracy compared to conventionally used measures.

We subsequently created the *Extubation AdvisorTM* (EA) as an extubation decision support tool incorporating the WAVE score to aid bedside clinicians with extubation assessments. The one-page EA report combines (i) enhanced predictive ability of extubation outcomes based on RRV, (ii) standardized SBT reporting with extubation readiness checklists, and (iii) individualized extubation failure risk mitigation strategies. From a functional perspective, there are two unique users of the EA tool. During a patient's SBT, an RT connects the patient's bedside monitor to a computer containing the EA software and enters clinical and demographic patient information through the EA user interface. An EA report is generated following the SBT and evaluated by the ICU MD to help inform their extubation decision. Thus, the EA tool provides a means for ICU MDs to objectively evaluate and communicate assessments of individual patient's readiness for extubation and an estimate of each patient's risk for extubation failure.

In 2019, we conducted a single centre, phase I mixed-methods observational study to evaluate our ability to generate EA reports and clinical impressions of EA, involving 117 critically ill patients with 151 SBTs and 80 extubations (currently under peer review). We demonstrated that 92% of EA reports could be generated and found an incidence of extubation failure of 11% in low-risk patients, 21% in high-risk patients, and 38% when both the RRV-derived model and clinical impression were high-risk. We assessed clinical impression of the EA tool using questionnaires and qualitative interviews with RTs and MDs involved in using the EA tool and making extubation decisions, finding that clinicians involved in using EA perceived that it had good potential to aid in extubation decision-making.

EA is a software tool that will directly influence clinician decision-making, with short-term consequences for the patient; thus, as per Health Canada requirements, EA must be regulated as a medical device. In addition, to implement EA in a broad sense, it must be integrated into bedside monitors or ventilators, with reports available to the electronic health record. Therefore, commercialization and regulatory approval are both required for clinical adoption. To accomplish this, Therapeutic Monitoring Systems (TMS), was founded by one of the co-PIs of this study, [name], in order to help bring EA (and similar) products to the bedside. All TMS products are based on the combination of variability analysis and machine learning to create variability-derived predictive analytics. EA has been submitted in August 2020 for approval by Health Canada in the Interim Order (IO) program. In addition, submission to the FDA is planned for March 2021.

A large evidence gap exists regarding the epidemiology of extubation failure in critically ill adults that poses several clinical dilemmas for ICU clinicians involved in liberating patients from ventilators, particularly if they are afflicted by COVID-19. The proposed study will evaluate the feasibility and initial perceptions of EA implementation in the intensive care unit by evaluating the feasibility of patient enrolment and consent, data collection, and EA report generation and delivery, with the aim to aid bedside decision-making, enhance care delivery, improve patient outcomes, and inform the design of a future randomized controlled trial.

This study is part of the Ontario Bioscience Innovation Organization (OBIO) Early Adopter Health Network (EAHN). The aim of this network is to bridge the gap between research and procurement of novel technologies. Thus, following completion of the 3 month protocol, the underlying aim of the protocol is for clinicians and administrators at the participating centers to determine if they would (1) like to be an early adopter of EA (i.e. license the product at the conclusion of the study based on highly

favourable experience), or (2) would like to continue participating in research regarding EA (i.e. participate in a planned future pilot then definitive randomized controlled trial), or (3) do not wish to continue with any further evaluation of the EA tool (e.g. if for example, the tool does not function with the existing care pathways in their ICU).

2.2. Background and rational for mixed-methods analysis

Incorporating the Extubation Advisor tool meaningfully into practice will amount to implementation of a complex intervention, as defined by standard guidance on the topic²⁵. Implementation of such interventions in the past has typically not been clearly described, designed systematically, or informed by theory of behaviour change²⁶, which has likely contributed to the relatively small likelihood of success of these interventions²⁷. We will engage in a systematic, theory-informed development process informed by two complementary frameworks²⁸: French's approach for theory-informed intervention development²⁹, and User Centered Design³⁰.

The French framework for intervention development describes a stepped approach based on 4 guiding questions: 1) Who needs to do what differently? 2) Using a theoretical framework, which barriers and enablers need to be addressed? 3) Which behaviour change techniques and modes of delivery are best suited to overcome barriers? 4) How can the behaviour(s) be measured and understood? User-Centred Design (UCD) describes an iterative process of design, evaluation, analysis, and re-design intended to result in a final product that meets pre-determined usability goals (e.g. 90% of the time, physicians should be able to read, understand, and make an extubation decision based on the EA report in less than 5 minutes). UCD has been shown in a variety of contexts to improve user satisfaction³¹, reduce errors in navigation and the resulting confusion^{30,32}, and to increase the efficiency with which the information can be found, understood, and used³³. Together, these frameworks can be employed to identify and rectify barriers and drivers to use of EA, as well as ensuring that the tool itself is optimally clear and useful for extubation decision-making.

3. Conflict of Interest

Therapeutic Monitoring Systems (TMS) is the commercial partner of the Dynamical Analysis Laboratory (DAL) within the Ottawa Hospital Research Institute, as TMS owns the rights to the intellectual property developed by the DAL. Several issued and pending patents form the DAL IP portfolio, including a patent underlying the technology of Extubation Advisor (US Patent 9,785,745 B2; issued Oct 10, 2017). [name] is one of the inventors of the patent, is Founder and CEO of TMS, and is Director of the DAL. In addition, [name] is one of the inventors related to the EA patent. The EA patent is owned by the OHRI, and TMS and OHRI have a partnership agreement as well as IP option agreement in place. TMS, DAL and the OHRI share the same objective, namely the development and commercialization of novel variability-derived clinical decision support tools in order to improve care.

To manage this conflict of interest (CoI), the following are in place: (1) [name] discloses the CoI in all grants, publications, presentations, and other public communication, and submits a CoI management agreement to the OHRI annually. (2) [name] will not be involved in recruitment of his own patients for this study. (3) All analyses performed by [name] and/or [name] within the DAL will be blinded to extubation outcomes. (4) [name] will supervise the analysis and interpretation of the

qualitative (i.e. interviews) results, and (5) [name], co-PI and co-chair the Steering Committee, will supervise the analysis and interpretation of the quantitative (i.e. analyses of feasibility) results of the study. In summary, transparency, public disclosure, scientific rigour, patient-centered focus, and independent oversight have been and continue to be the foundations for this CoI management.

4. Research Question

What is the feasibility and the initial perceptions of a novel extubation decision support tool, Extubation Advisor, in the intensive care unit (ICU) in multiple centers?

5. Objectives

The primary research objectives of this study are to:

1. Evaluate the feasibility of:
 - a. Patient enrolment and consent
 - b. Wave form data capture
 - c. Participant clinical data entry
 - d. Extubation Advisor report generation and delivery to physicians
2. Perform a mixed-methods analysis of physicians and respiratory therapists regarding usability, perceived value, identified behaviours, perceived barriers and drivers, and perceived impact.

The secondary research objective of this study is to:

1. Evaluate the feasibility of completing the clinical case report form (CRF).

6. Study Outcomes

Primary objectives:

1. Implementation of Extubation Advisor will be considered feasible if:
 - a. >50% of identified eligible patients are enrolled and consented,
 - b. >75% of the time, wave form data is captured,
 - c. >90% of the time, participant clinical data is fully entered into the EA tool,
 - d. >80% of the time, an extubation report is successfully generated and delivered to the attending physician.
2. Usability, perceived value, identified behaviours, perceived barriers and drivers, and perceived impact will be assessed through interviews with RTs and MDs.

Secondary objectives:

1. Completion of the clinical CRFs will be considered feasible if >90% of clinical CRFs are complete.

7. Design

This is an open-label, multi-center interventional Phase 1 study to implement and evaluate perceptions of Extubation Advisor in consenting patients in the intensive care unit.

8. Centers

This study will be conducted at two Ontario academic hospitals: The Ottawa Hospital and Unity Health Toronto.

9. Sample Size and Timeline

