The EA system will process the portions of CO₂ waveforms and vital signs data corresponding to the SBT and proceed to clean and assess the quality of the data, compute variability metrics, and generate a score summarizing the risk of extubation failure.

The RT will then put the PS/PEEP back to normal on the ventilator and complete the SBT Outcome Information and their own impression of the risk of extubation failure (<2 min). The RT will click on the “Generate Report” button, which displays a PDF report on screen. The RT will then review the report with the attending physician and determine whether to proceed with the extubation or not. If desired, the EA report may be emailed to a secure hospital email with the actual report attached for printing, so that

the RT may physically give the report to the attending MD, or place it at the bedside. This process may be repeated every time an SBT is repeated for assessment of a patient’s readiness for extubation, until the patient undergoes planned extubation, or reaches an alternate outcome (self-extubation, direct to tracheostomy, death, transfer to another institution). RTs who complete EA data entry during the SBT will receive a \$10 coffee gift card, limited to a maximum of 3 gift cards per patient for repeated SBTs, as a token of appreciation for their time and expertise.

After a minimum of 72 hours after extubation, the site Research Coordinator will complete a short **Clinical Outcome CRF**, which will include the time of extubation, the outcome of extubation, the need and timing of re-intubation (if present), the need for non-invasive ventilation or high flow heated humidity, all within the 72 hours post-extubation. Last, the Clinical Outcome CRF will include the date of ICU discharge and the status of the patient at that time. Patients who remain hospitalized at 72 hours will be followed via their electronic medical record until hospital discharge.

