11.2. Definition of complete CRF

A patient and their data collection will be deemed “complete” if **(1)** the patient’s last SBT prior to extubation resulted in the generation of an EA report that was shown to the physician, and **(2)** the clinical outcome CRF is complete. In cases where the completion of the “Clinical Outcome Information” CRF is not possible (e.g. when extubation did not follow the generation of an EA report, if a tracheostomy was performed, etc.) the patient will remain enrolled, but results will not be included in final analyses, and those patients will be deemed incomplete. Funding will thus prioritize complete patient data collection. Additional funding will be provided if multiple SBTs are captured in the same patient.

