12.1. Feasibility evaluation of Extubation Advisor

To evaluate the feasibility of Extubation Advisor implementation we will quantify:

1. The number of identified eligible patients enrolled and consented to capture the proportion of both (a) patients enrolled and (b) patients not enrolled due to patient/caregiver refusal.
2. The proportion of useable recordings and data fully entered, and report on the reasons for failure.
3. The number of reports successfully generated and transmitted to physicians, and report on the reasons for failure.

To evaluate the feasibility of completing clinical CRFs we will quantify the number of clinical CRFs that have been deemed complete.

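### The secondary outcome is meant to measure completion of the clinical CRF, but the only definition of a complete CRF also requires an EA report shown to the physician, and no denominator is given (minor)

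*Combined protocol and SAP*

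**What the plan says.** The secondary objective in Section 5 is to "Evaluate the feasibility of completing the clinical case report form (CRF"). Section 6 turns it into a threshold: "Completion of the clinical CRFs will be considered feasible if >90% of clinical CRFs are complete". For the evaluation, Section 12.1 says only that "we will quantify the number of clinical CRFs that have been deemed complete". That is a count, with no denominator.

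Completeness is defined once, in Section 11.2, whose heading says it defines a complete CRF. Under it, a patient and their data are complete if two conditions hold. Condition (1) is that the last "SBT prior to extubation resulted in the generation of an EA report that was shown to the physician". Condition (2) is that the clinical outcome CRF is complete. For cases where the form cannot be completed (the examples are "when extubation did not follow the generation of an EA report, if a tracheostomy was performed, etc"), Section 11.2 adds that "the patient will remain enrolled, but results will not be included in final analyses, and those patients will be deemed incomplete".

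Two other places bear on this. Section 11.1 makes the form due after extubation: "After a minimum of 72 hours after extubation, the site Research Coordinator will complete a short" outcome form. Primary outcome 1d in Section 6 already covers reports: ">80% of the time, an extubation report is successfully generated and delivered to the attending physician".

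**The concern.** The objective asks whether site staff can complete a short outcome form. Condition (1) concerns something else, namely whether the software produced a report and the physician saw it. If Section 11.2 is the scoring rule, a form with every field filled in counts as a failure whenever the report failed. A result of not feasible could then reflect only report failures, which 1d already measures, and would say nothing about the form itself.

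The missing denominator adds a second choice. Patients with no possible form are both deemed incomplete and left out of the final analyses. They could be counted as failures or dropped. With two readings of the numerator and an open denominator, the same data could be reported as feasible or not feasible depending on a choice made afterwards. This matters because the study is meant to inform a later randomised trial, and that trial would rely on outcome forms.

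**Working it through.** **Plan's own figure.** Section 9.1 enrols 72 and expects a 20% loss: 72 × 0.80 = 57.6, rounded to 58 patients with complete CRFs. This reproduces. The loss pools protocol deviation, lost data and forms that cannot be completed, so 58 fits the patient-level idea in Section 11.2 and is not a forecast of form completion.

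**Numerator.** For a patient extubated after an SBT, the two readings compare as follows.

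| Report shown at last SBT | Outcome form filled in | Two-part reading | Form-only reading |
|---|---|---|---|
| yes | yes | complete | complete |
| no | yes | incomplete | complete |
| yes | no | incomplete | incomplete |
| no | no | incomplete | incomplete |

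The readings differ only in the second row. Over a fixed set of extubated patients, the two-part rate therefore cannot exceed the proportion with a report shown at the last SBT.

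**Denominator.** Patients never extubated have no form due. Over all enrolled patients they count as failures; over extubated patients they do not appear. If every patient deemed incomplete were dropped, the rate would be 100% by construction.

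**Size, as an illustration.** Inputs:
- Forms due: n = 72 (assumption: every enrolled patient is extubated).
- Report available at the last SBT: 92%. Section 2.1 gives this for report generation in the earlier single-centre study; using it for reports shown at the last SBT is an assumption.
- Form completion: 95% (assumption).
- Report and form completion independent (assumption).

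Threshold: 0.90 × 72 = 64.8, so at least 65 are needed (65/72 = 90.3%; 64/72 = 88.9%).

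Two-part rate: 0.92 × 0.95 = 0.874. For the expected two-part rate to exceed 90%, form completion would have to exceed 0.90/0.92 = 97.8%.

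The chance of passing is the exact binomial P(X ≥ 65 | n = 72, p), with p equal to the two-part rate or to the form-completion rate:

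| Form completion (assumed) | Two-part rate | Chance of passing, two-part | Chance of passing, form-only |
|---|---|---|---|
| 90% | 82.8% | 6% | 57% |
| 95% | 87.4% | 30% | 97% |
| 98% | 90.2% | 59% | >99% |
| 100% | 92.0% | 78% | 100% |

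Sensitivity to the number of forms due: both conditions in Section 11.2 presuppose extubation, so the plan's 58 complete patients imply at least 58 extubated. With n = 58, 0.90 × 58 = 52.2, so 53 are needed. At 95% form completion the chances are P(X ≥ 53 | 58, 0.874) = 25% and P(X ≥ 53 | 58, 0.95) = 93%. The gap is of the same order.

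**The case against.** The strongest reply is that Section 11.2, despite its heading, defines a complete patient. The subject of its main sentence is the patient and their data collection. The outcome form appears as a separate second condition, which would be circular if a complete CRF meant both. Sections 5 and 6 speak only of the clinical CRF. The two-part link rests on the heading and on the shared word for deeming something complete. This stands, and two-part scoring cannot be presented as settled. What remains is that Section 12.1 points to a completeness rule, Section 11.2 is the only one, and no form-only rule is written down.

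It is also fair that Section 12.1 requires reasons for report failures, so a careful reader could separate these from form failures. That limits the harm but does not fix the stated pass or fail result.

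A reader might infer more than the documents support, in three ways:
- *That the two-part rate is capped by the report rate over any denominator.* The cap holds over a fixed set of extubated patients. It fails if patients without a report leave the denominator.
- *That passing 1d between 80% and 90% forces the secondary criterion to fail.* 1d can be read per SBT, and SBTs may be repeated, whereas condition (1) concerns only the last one. At the earlier study's ratio, 72 × 151/117 gives about 93 SBTs. Suppose ten reports fail, four of them at a last SBT, with all 72 patients extubated and all forms complete. Then 1d is 83/93 = 89.2%, the secondary is 68/72 = 94.4%, and both pass.
- *That the plan expects to fail its own criterion, because 58/72 = 80.6% and 65 are needed.* The 20% loss is pooled over several causes, and the comparison needs all enrolled patients as the denominator, which the plan does not state.

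**Conclusion.** The concern holds as a minor point. Followed as headed, the only completeness rule can score a fully completed form as a failure and so does not answer the secondary objective. The alternative form-only reading is open but not stated, and neither reading has a denominator. Under the assumptions above (72 forms due, 92% reports, 95% form completion, independence), the choice of reading moves the chance of meeting >90% from about 97% to about 30%. These figures show that the wording can decide the result; they are not a forecast. The four primary feasibility criteria are unaffected.

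**What to change.** - **Sections 6 and 12.1:** score the secondary outcome on completion of the Clinical Outcome CRF alone, which is condition (2) of Section 11.2. Keep the >90% threshold. Take as denominator all enrolled patients who were extubated, planned or self-extubated, whether or not an EA report was generated. Report the number of enrolled patients with no form due, by reason.
- **Section 11.2:** rename the two-part measure *complete patient* and report it separately over all enrolled patients. State that exclusion from the final analyses does not remove extubated patients from the secondary denominator.
- **Section 9.1:** describe the 58 as complete patients instead of patients with complete CRFs.

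The cost is wording in four sections. The sample size and threshold stay as they are. The one consequence is that the two-part rate becomes a separate descriptive figure.
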